5.6. RESTRICTIONS

In order to obtain reliable safety and efficacy results from the study, participants will be requested to refrain from undergoing any additional unnecessary periodontal treatments during the course of the study, aside from those provided as part of the study.

In cases that such additional treatment is deemed necessary, the participants will be requested to report the treatment details to the study investigators, who will record them.

Participants will also be requested to follow the instructions on maintaining good oral hygiene they receive from the investigators at the beginning of the study, and refrain from changing this routine. An exception will be made during the 2 days following treatment with Pocket-X Gel, during which participants treated with the product will be requested to brush their teeth very gently and not use dental accessories such as dental floss, in accordance with the manufacturer's instructions.

6. STUDY POPULATION

6.1. INCLUSION CRITERIA

In order to be found eligible to participate in this study, an individual must meet all of the following criteria:

1. Provision of signed and dated informed consent form
2. Male or female, aged 18 and above
3. Provision of up-to-date full mouth periapical x-rays
4. Participants suffering from active moderate to severe chronic periodontitis with at least 3 sites of periodontal pockets of 5 mm or greater depth in each quadrant.
5. Participants with a minimum of 6 teeth with periodontal pocket depth of more than 5 mm.
6. Participants with a minimum of 20 teeth

6.2. EXCLUSION CRITERIA

An individual who meets any of the following criteria will be excluded from participation in this study:

1. Known hypersensitivity to any of the device's components as listed on the user leaflet
2. Pregnancy or lactation
3. Smoking of more than 9 cigarettes per day
4. A concurrent dental disease, except for periodontitis, or planned treatment that may interfere with the study or study intervention, such as dental surgery, teeth implantation, etc.
5. Chronic disease such as diabetes mellitus or rheumatoid arthritis
6. Aggressive periodontitis
7. History of radiotherapy or chemotherapy

8. Mucosal immune disease
9. Mental disorders
10. Parafunctional habits such as bruxism
11. Participant has taken antibiotics during the previous 6 months
12. Participant has undergone periodontal treatment during the previous 12 months

6.3. SCREEN FAILURE

Screen failures are defined as participants who consent to participate in the clinical trial but do not meet one or more criteria required for participation during the screening procedures. These participants will not be included in the study.

6.4. INFORMED CONSENT

Participants will be requested to sign an informed consent form, which will be pre-approved by the study's ethics committee, prior to enrollment into the study. Only participants who signed the informed consent form may be enrolled.

7. PARTICIPANT DISCONTINUATION/WITHDRAWAL

Participants are free to withdraw from participation in the study at any time upon request. An investigator may discontinue or withdraw a participant from the study for the following reason:

- Participant meets one or more of the exclusion criteria
- Participant has an interproximal Plaque Index of more than 30% after up to two initial sessions of prophylaxis and instruction, indicating that the participant does not follow investigator's dental hygiene instructions
- Serious adverse event
- Medical condition that prohibits the patient from continued participation in the study

8. LOST TO FOLLOW-UP

A participant will be considered withdrawn due to lost to follow-up if he or she fails to show up for one of the visits and is unable to be contacted by the study site staff/investigators.

Before a participant is deemed lost to follow-up, the site staff/investigators will make every effort to regain contact with the participant and reschedule the missed visit.

9. STUDY ASSESSMENTS

9.1. EFFICACY ASSESSMENT

The following measurements will be recorded during the study, and will be used to assess the efficacy of the intervention:

- Plaque index
- Pocket probing depth
- Bleeding index
- Recession level
- Clinical attachment level
- Mobility grade
- Furcation
- Specific periodontal bacteria quantification [optional]

The above measurements will be recorded at baseline and at follow-up visits for each participant. The values will be recorded separately for each periodontal pocket. .

Efficacy data from follow-up visits will be compared to the baseline values in order to obtain the efficacy results. The efficacy results will be compared between treated periodontal pockets and control periodontal pockets and to data obtained from available literature.

9.2. SAFETY ASSESSMENT

Safety assessment will be conducted based on adverse events reported by the study participants as well as any new pathologies observed by the investigators during visits that did not exist at baseline or have worsened since baseline. Such observations will also be regarded as adverse events.

Safety assessment will be conducted by analyzing the adverse events, their quantity, severity, duration and their connection to the studied device. In case that the adverse event is localized, these parameters will be compared between the segment(s) treated with Pocket-X Gel and the untreated segments of the same patient. Adverse events will also be compared to adverse events reported during scaling and root planing studies, based on available literature.

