12. ADVERSE EVENTS

During each visit, participants will be asked whether they experienced or experience any adverse events. In case that an adverse event has occurred, investigators will record all details of the event and will assess whether the event may be related to the studied device.

Any new pathologies observed by the investigators that did not exist at baseline or have worsened since baseline, will be considered adverse events and recorded accordingly.

Participants will be requested to report any serious adverse events immediately to the investigators, without waiting for the next visit.

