12.2. CLASSIFICATION OF ADVERSE EVENTS

Each adverse event that occurs during the study will be classified by the investigator(s) in terms of severity, relation to the studied device and expectedness. The classification of an adverse event may be updated as new relevant information, that may have an influence on the classification, becomes available.

Severity: adverse event's severity will be classified in accordance with the following:

- **Mild** – events that require minimal or no treatment and do not interfere with the participant's daily activities.
- **Moderate** – events that result in a low-moderate level of inconvenience and may cause some interference with functioning.
- **Severe** – events that interrupt a participant's usual daily activity and may require systemic drug therapy or other treatment. Severe events are usually potentially life-threatening or incapacitating, however, the term "severe adverse event" does not necessarily equate to "serious adverse event".

Relation to studied device: adverse event's relation to the studied device will be classified in accordance with the following:

- **Definitely related** - this classification will be applied if there is clear evidence to suggest that the adverse event is related to treatment with the studied device, and other possible contributing factors can be ruled out. For this classification to be applicable, the adverse event, including an abnormal laboratory test result, should be an event that occurred within a reasonable time following treatment with the studied device and the event cannot be explained by other factors such as concurrent disease or other drugs, chemicals, treatments or lifestyle.
- **Probably related** - this classification will be applied if there is evidence to suggest that the adverse event is related to treatment with the studied device, and the influence of other factors is unlikely. For this classification to be applied, the adverse event, including an abnormal laboratory test result, should be an event that occurred within a reasonable time following treatment with the studied device, and the event is unlikely to be attributed to other factors such as concurrent disease, drugs, chemicals, treatments or lifestyle.

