All AEs will be coded using coding dictionaries MedDRA (most updated version) and will be

summarized by system organ class (SOC) and preferred term (PT).

AEs will be listed individually including SOC, PT, seriousness of event, onset and resolution dates, duration, severity, relationship to the study treatment, action taken and outcome.

Frequency AEs and treatment-related adverse events will be summarized in tables by SOC, PT and treatment and by seriousness.

In case that the adverse event is localized, frequency of local AEs will be compared between the segment(s) treated with Pocket-X Geland the untreated segments of the same patient using Chi-square test or Fisher's Exact test (as is appropriate).

Adverse events will also be compared to adverse events reported during scaling and root planing studies, based on available literature. Chi-square test or Fisher's Exact test (as is appropriate) will be used for comparison in incidence of events.

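### Section 9.2 compares device-relatedness of local adverse events between gel and untreated segments, although relatedness is rated only to the gel, so this one comparison reflects attribution and not harm

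*Combined protocol and SAP*

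**What the plan says.** Section 9.2 defines the safety analysis: "Safety assessment will be conducted by analyzing the adverse events, their quantity, severity, duration and their connection to the studied device". The next sentence says that, for a localized event, "these parameters will be compared between the segment(s) treated with Pocket-X Gel and the untreated segments of the same patient". On a plain reading, relatedness is one of the compared parameters.

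Relatedness is rated against one thing. Under section 12 the investigator "will assess whether the event may be related to the studied device". Section 12.2 states that "adverse event's relation to the studied device will be classified in accordance with the following", and each of its five categories is worded around treatment with the device. There is no parallel rating for scaling and root planing (SRP), which section 5.1 gives to the whole mouth. Section 5.1 also makes the study open-label, so the rater knows which segments received gel.

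Section 15.2 then does two separate things:

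- A descriptive table: "Frequency AEs and treatment-related adverse events will be summarized in tables by SOC, PT and treatment and by seriousness".
- A formal comparison, by chi-square or Fisher's exact test, in which "frequency of local AEs will be compared between the segment(s) treated with Pocket-X" Gel and the untreated segments. It is not restricted to related events.

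The individual listing in 15.2 includes "relationship to the study treatment, action taken and outcome". The documents do not define study treatment separately from the device.

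**The concern.** A comparison between sides is informative only if the same rule produces the count on each side. Here it does not. A local event in a gel-treated segment can be rated possibly, probably or definitely related to the gel. The same event in a segment without gel will seldom be rated so, because the rater knows that no gel was placed there and the two upper categories in 12.2 require a reasonable time relation to treatment with the device. Local events on both sides are foreseeable: section 3.3 itself expects pain, bleeding and swelling of the gums after SRP.

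The related-event columns would then differ because of how events are labelled. With equal true rates of local events, the table could still look like harm from the gel. The distortion runs against the product and does not hide harm, but it could mislead a reader about safety.

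**Working it through.** **Inputs.** N = 34 enrolled (sections 5.4 and 15.1). This reproduces: a one-sided paired t-test at 5% with effect size 0.5 needs 27 completers (power 81.2%), and 27/(1 - 0.20) = 33.75, rounded up to 34. The documents give no local event rate and no share of events rated related. Both are assumptions here:

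- r = proportion of participants with a local event, the same on both sides
- q = share of gel-side events rated at least possibly related, taken as 0.5

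**Step 1: expected counts.** All-cause events per side are N x r. Related events on the gel side are N x r x q. At r = 0.30, all-cause events are 34 x 0.30 = 10.2 on each side. Related events on the gel side are 10.2 x 0.5 = 5.1. If 0% to 5% of untreated-side events were rated related, the other column would hold 0 to 0.5.

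**Step 2: a yardstick for an apparent excess.** The plan names no test for related events, so these p-values are only illustrative. Two-sided Fisher's exact test, N = 34 per side:

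| Gel v untreated | p |
|---|---|
| 5 v 0 | 0.053 |
| 6 v 0 | 0.025 |
| 6 v 1 | 0.105 |
| 7 v 1 | 0.054 |

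Fisher's test treats the sides as independent. The paired counterpart, exact McNemar, gives 2 x 0.5^6 = 0.031 for 6 v 0.

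**Step 3: chance of reaching 6 related gel-side events with equal true rates.** P(X >= 6), X ~ Binomial(34, r x 0.5):

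| r | Expected related, gel side | P(X >= 6) |
|---|---|---|
| 10% | 1.7 | 0.6% |
| 15% | 2.55 | 3.9% |
| 20% | 3.4 | 12% |
| 30% | 5.1 | 40% |
| 50% | 8.5 | 89% |

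**Step 4: sensitivity to the untreated side.** With no related events there, the figures in step 3 are also the chances that Fisher's test would show a gel-side excess at p <= 0.05. If 5% of untreated-side events are rated related, those chances fall from 12% to 9% (r = 20%), from 40% to 29% (r = 30%) and from 89% to 70% (r = 50%).

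**Step 5: sensitivity to q.** At r = 20% with a quarter of events labelled related, r x q = 0.05 and the chance is 0.6%. At r = 30% with q = 0.8 it is 86%, or 73% with 5% rated related on the untreated side.

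**Step 6: the all-cause comparison already in 15.2.** Under equal rates, the chance that Fisher's test shows a significant gel-side excess in all local events is 0.6% to 1.3% for r from 10% to 50%. Attribution does not enter.

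**The case against.** The best defence is that the plan already contains the right comparison. The only between-segment safety test named in 15.2 uses all local events whatever their attribution. Related events are only tabulated, and section 4 defines the safety objective by adverse events and oral pathologies, without mentioning relatedness. A reader would also see the all-cause result beside the related-event table and might find a device-relatedness column for a segment without device self-explanatory. All of this stands, and it limits the weight of the point. It does not remove it, because 9.2 still prescribes the comparison and 15.2 still calls for the table by treatment.

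A reader might infer three stronger things that the documents do not support:

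- **That the formal safety test is biased.** It is not. No hypothesis about related events is stated anywhere, so no planned test has a null that is false by design.
- **That the untreated side is fixed at zero.** Nothing bars a device-related rating there. Section 3.2 says the gel may be ejected from the pocket, and 12.2 allows the lowest category only with a documented definitive alternative cause. The count should be low, and one such event moves 6 v 0 (p = 0.025) to 6 v 1 (p = 0.105).
- **That SRP cannot be recorded as a cause.** Section 12.2 has the rater weigh other treatments, so SRP can be documented as the alternative cause. What is missing is a separate SRP rating on the same scale.

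**Conclusion.** The point holds, within limits. For relatedness alone, the comparison stated in 9.2 and the by-treatment table in 15.2 reflect a rating that refers only to the gel and is made by an unblinded investigator. They can show an apparent gel-side excess when true local event rates are equal. The planned comparison of all local events is sound in this respect.

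The size cannot be fixed from the documents. With half of gel-side events labelled related, the effect is negligible if about 10% of participants have a local event per side (0.6%) and large if about half do (89%). These figures assume equal true rates, independent participants and 34 evaluable on each side. Reading them as chances of a significant excess also assumes no related events on the untreated side and a test that the plan does not specify.

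**What to change.** 1. In 9.2, remove connection to the device from the parameters compared between segments. The section then agrees with the all-cause comparison of local events already in 15.2.
2. In 15.2, report device-relatedness of local events for gel-treated segments only, without a control column.

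The all-cause test in 15.2 needs no change on this account. If a side-by-side attribution table is wanted, each local event could also be rated for relation to SRP on the same five-level scale. That is optional.

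Cost: wording in two sections. The optional rating adds one field to the adverse-event form. No extra participants or visits are needed.

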10. CALIBRATION OF EXAMINERS

The study's investigators – two experienced periodontists, will be calibrated for scaling and root planning procedures and recordings of clinical data to ensure that all clinical procedures will be standardized according to the study protocol and to minimize both intra and inter-examiner variability across the time points. The two examiners will be calibrated initially for PPD and CAL according to the method of Jeffcoat et al. (1). Briefly, as part of the calibration exercise, each of the 2 examiners will measure PPD and CAL 2 time at 10 sites (PPD>5 mm) in each of 5 patients. For both examiners and all 25 sites, the mean absolute will be <0.5 mm for both parameters.

12. ADVERSE EVENTS

During each visit, participants will be asked whether they experienced or experience any adverse events. In case that an adverse event has occurred, investigators will record all details of the event and will assess whether the event may be related to the studied device.

Any new pathologies observed by the investigators that did not exist at baseline or have worsened since baseline, will be considered adverse events and recorded accordingly.

Participants will be requested to report any serious adverse events immediately to the investigators, without waiting for the next visit.

12.1. DEFINITION OF ADVERSE EVENTS

Adverse event means any unfavorable or unintended medical occurrence associated with the study, whether or not considered intervention-related.

Serious adverse event means any adverse event that results in the following outcomes: death, a life-threatening adverse event, inpatient hospitalization, a persistent or significant incapacity, substantial disruption of the ability to conduct normal life functions or congenital anomaly/birth defect. Important medical events that may not result in death, be life-threatening, or require hospitalization may be considered serious when, based upon appropriate medical judgment, they may jeopardize the participant and may require medical or surgical intervention to prevent one of the outcomes listed in this definition.

12.2. CLASSIFICATION OF ADVERSE EVENTS

Each adverse event that occurs during the study will be classified by the investigator(s) in terms of severity, relation to the studied device and expectedness. The classification of an adverse event may be updated as new relevant information, that may have an influence on the classification, becomes available.

Severity: adverse event's severity will be classified in accordance with the following:

- **Mild** – events that require minimal or no treatment and do not interfere with the participant's daily activities.
- **Moderate** – events that result in a low-moderate level of inconvenience and may cause some interference with functioning.
- **Severe** – events that interrupt a participant's usual daily activity and may require systemic drug therapy or other treatment. Severe events are usually potentially life-threatening or incapacitating, however, the term "severe adverse event" does not necessarily equate to "serious adverse event".

Relation to studied device: adverse event's relation to the studied device will be classified in accordance with the following:

- **Definitely related** - this classification will be applied if there is clear evidence to suggest that the adverse event is related to treatment with the studied device, and other possible contributing factors can be ruled out. For this classification to be applicable, the adverse event, including an abnormal laboratory test result, should be an event that occurred within a reasonable time following treatment with the studied device and the event cannot be explained by other factors such as concurrent disease or other drugs, chemicals, treatments or lifestyle.
- **Probably related** - this classification will be applied if there is evidence to suggest that the adverse event is related to treatment with the studied device, and the influence of other factors is unlikely. For this classification to be applied, the adverse event, including an abnormal laboratory test result, should be an event that occurred within a reasonable time following treatment with the studied device, and the event is unlikely to be attributed to other factors such as concurrent disease, drugs, chemicals, treatments or lifestyle.
- **Possibly related** - this classification will be applied if there is some evidence to suggest that the adverse event is related to treatment with the studied device but it's possible that other factors have caused or contributed to the event, such as concurrent disease, drugs, chemicals, treatments or lifestyle.
- **Unlikely to be related** - this classification will be applied if it is deemed improbable that the adverse event is related to treatment with the studied device (e.g., the event did not occur within a reasonable time following treatment), or in cases which other factors, such as concurrent disease, drugs, chemicals, treatments or lifestyle provide plausible explanations for the event.
- **Not related** - this classification will be applied if the adverse event is deemed to be completely independent of treatment with the studied device, and/or evidence exists that the event is definitely related to another etiology. There must be an alternative, definitive etiology documented by the investigator.

Expectedness: an adverse event will be considered unexpected if the nature, severity or frequency of the event is not consistent with the risk information previously described for the studied device.

12.3. DOCUMENTATION OF ADVERSE EVENTS

All adverse events will be documented by study investigators or study staff on the participant's Case Report Form. Information to be collected includes event description, time of onset, treatment given, clinician's assessment of severity, relationship to studied device

(assessed only by those with the training and authority to make a diagnosis), whether the event is expected and time of resolution/stabilization of the event. All adverse events occurring during the course of the study will be documented appropriately regardless of relatedness to the studied device. All adverse events will be followed to adequate resolution.

Any medical condition that is present at the time that the participant is screened will be considered as baseline and not reported as an adverse event. However, if the study participant's condition deteriorates at any time during the study, it will be recorded as an adverse event.

